#### **3.7 Sample size Determination**

#### Sample size for participants with Metabolic Syndrome (Primary outcome variable)

Using Power analysis computation of sample size with G.Power 3.1.9.4 software. The estimates will be based on a significance level of 5% and power of 80% to detect a difference between-group of 0.20 in MetS prevalence after 3 months intervention. A sample size of 98 is obtained. After accounting for design effect the sample size is 104. Assuming a dropout rate and failure to consent rate of 10%, 120 participants will be needed in total. 60 participants in the intervention and 60 in the non- intervention groups.

#### Sample selection

**Sampling Procedure:** A purposive sample of females with Metabolic Syndrome in Wakiso from the baseline study undertaken in Wakiso district will be followed up in the community, screened and invited for participation in the study at baseline.

#### **Randomization: Sequence generation**

The randomization procedure will be automatically performed by a biostatistician to minimize the differences between the two groups for all stratifying variables. Using a computer random number generator a randomisation list of permuted blocks of size 8 with an allocation ratio of 1:1 will be generated. Then the participants will be randomly allocated to either the intervention arm (60) or the control group (60) and followed up for 3 months.

#### **Randomization: Allocation Concealment**

Random allocation will be conducted with minimization algorithm centrally in a single step to obtain two lists of nominative data. The allocation concealment will be by sealed opaque envelop to preserve allocation concealment. The biostatistician will assign numbers to the envelopes from 1 to 120. This will help prevent the possibility for researchers to predict or influence the allocation of participants. Due to practical reasons, we shall obtain informed consent after the randomization process.

The study coordinator who will be blinded to the randomisation allocation list will enrol the participants. The numbered envelopes will be distributed in sequence from 1 to 120 to a list of names from the baseline survey diagnosed with Metabolic Syndrome. This list of names will be generated after randomisation of those names.

All the individuals belonging to the intervention group will be separated from the individuals belonging to the control group and two allocation lists will be generated with control and intervention groups. The principal investigator will then follow up and identify the study participants in their respective villages, with the assistance of the village chairpersons.

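### The protocol names two allocation methods for the same 120 women, and the one it describes in detail does not secure the covariate balance it claims

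*Protocol*

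**What the plan says.** Both statements stand in the current text of Protocol section 3.7.

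- **Randomization: Sequence generation.** The biostatistician's procedure is meant "to minimize the differences between the two groups for all stratifying variables". The means given is a block list: "Using a computer random number generator a randomisation list of permuted blocks of size 8 with an allocation ratio of 1:1 will be generated". The target is 60 women per arm.
- **Randomization: Allocation Concealment.** "Random allocation will be conducted with minimization algorithm centrally in a single step to obtain two lists of nominative data". The same subsection then sets out the execution: "The numbered envelopes will be distributed in sequence from 1 to 120 to a list of names from the baseline survey diagnosed with Metabolic Syndrome". On the order of the names it adds: "This list of names will be generated after randomisation of those names".

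The protocol names no stratifying or minimisation variable. It describes no stratum-specific list, imbalance measure or assignment probability, and it does not say that one method replaces the other or how the two combine.

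**The concern.** A permuted-block list fixes the k-th assignment before anyone looks at the k-th woman. Minimisation computes her assignment from her own covariates and those of women already placed. One assignment cannot come from both, so a reader cannot tell which method will be run, reproduce it, or know which factors the analysis should carry.

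The execution steps fit the block list. But that list is single and unstratified, and it is applied to names in random order, so nothing in it acts on a covariate. The balance claim is then empty.

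Two things are at stake:

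- **Precision.** Every participant starts with MetS (section 3.4), and MetS means at least 3 of 5 components (section 3.6). A woman with exactly 3 must lose one component to resolve; a woman with 5 must lose three. Baseline component count is therefore a plausible prognostic factor by construction. Under the single list its balance is left to chance.
- **Analysis.** If factors are balanced by design but left out of the primary comparison, the unadjusted standard error is too wide.

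**Working it through.** **1. Reproduce the stated arm sizes.** Inputs from section 3.7: 120 envelopes, block size 8, ratio 1:1. Blocks: 120 / 8 = 15, all complete. Per arm: 15 × 4 = 60. The stated 60:60 follows exactly from the block list.

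**2. Match the execution to each method.** Envelopes numbered in advance and handed out in order to a shuffled list of names are how a block list is run. If minimisation were used, each envelope would have to be tied to a particular woman, and the shuffled sequence would have no role. Two resulting lists of names, one per arm, are compatible with either method.

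**3. Covariate balance under each scheme.** 4,000 simulated allocations of 120 women, looking at one binary covariate. Assumptions not in the protocol: prevalence 50% or 30%; minimisation on three binary factors with a biased coin of 0.8. Entries are the absolute between-arm difference in the number of women with the covariate: mean / 95th percentile / probability of 10 or more.

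| Scheme | Prevalence 50% | Prevalence 30% |
|---|---|---|
| Single list, blocks of 8, random name order | 4.4 / 11 / 8.2% | 3.9 / 10 / 5.6% |
| Plain 60:60 randomisation | 4.4 / 11 / 8.1% | 4.0 / 10 / 5.7% |
| Blocks of 8 stratified by the covariate | 0.9 / 2 / 0% | 0.9 / 2 / 0% |
| Minimisation | 1.2 / 3 / 0% | 1.2 / 3 / 0% |

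The first two rows agree to within simulation error. Blocking in a single list of all 120 women adds only the arm totals. Biased-coin minimisation gave exactly 60:60 in only about 54–55% of runs, whereas the block list always does.

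**4. What this costs in precision.** Illustrative assumptions: 60% of women have exactly 3 components; MetS persists in 60% of them and in 90% of the rest (a 30-point gap).

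- SD of the between-arm difference in the 3-component share: √(2 × 0.6 × 0.4 / 60) = 0.0894, or 8.9 points.
- Contribution to the MetS difference: 0.0894 × 0.30 = 0.027, an SD of 2.7 points. At the edge of the 95% range: 1.96 × 0.0894 × 0.30 = 0.053, or 5.3 points.
- Overall persistence: 0.6 × 0.6 + 0.4 × 0.9 = 0.72. SE of the difference: √(2 × 0.72 × 0.28 / 60) = 0.082, or 8.2 points.
- Share of outcome variance explained: 0.30² × 0.24 / (0.72 × 0.28) = 0.0216 / 0.2016 = 0.107, about 11%.
- SE after balance and adjustment, on the risk-difference scale: √(1 − 0.107) = 0.945 of its former value, a cut of about 5.5%.

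With a 20-point gap (60% versus 80%), overall persistence is 0.68 and the share explained is 0.20² × 0.24 / (0.68 × 0.32) = 0.0096 / 0.2176 = 0.044. The SE falls by about 2%.

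**5. Arm sizes after stratifying by one two-level factor.** Only the last block in each stratum can be incomplete. Since 120 is a multiple of 8, remainders of r and 8 − r give a largest possible difference of 2 × min(r, 8 − r), which is at most 8 women (56:64). At a 72/48 split there is no remainder and the arms are exactly 60:60.

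**The case against.** Four objections carry weight.

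- **Minimisation is feasible here.** A reader might infer that it cannot work with a pre-made list. That holds for women enrolled one at a time. Here all names come from the survey database and are allocated centrally in one step, so batch minimisation could produce two lists. If that sentence governs, the balance aim could be met. The defect is that the text does not say which method governs, and the factors are unnamed either way.
- **The analysis does adjust for something.** The mixed model under Data Analysis adjusts for age, education, occupation and similar factors, so it would be wrong to say that covariates are ignored. But its listed outcomes are BP, WC, HDL-C, FBS and triglycerides, not MetS status, and those factors are not called stratifying variables.
- **Chance imbalance is not an error.** A reader might take 5.3 points, about a quarter of the 20-point target, as a distortion of the result. It is a tail value of random variation that the standard error already covers. Nor do the documents support calling component count the strongest predictor; its relevance follows only from the definition of MetS.
- **Balance on the list is not balance in the analysis.** Consent is taken after randomisation, and women attending under 60% of sessions are excluded. Stratifying the list does not protect the analysed groups from either. This limits what the fix can achieve but does not remove the contradiction.

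The word minimisation may simply be used loosely for ordinary blocked randomisation. The text does not settle that.

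**Conclusion.** The contradiction is in the text and rests on no assumption: two allocation methods for the same 120 women, with no statement of which applies. The procedure described in detail secures 60:60 and nothing more. On a covariate it performs like plain 60:60 randomisation (95th percentile 10–11 women, against 2–3 with stratified blocks or minimisation, at assumed prevalences of 30% and 50%), so the balance claim is unsupported.

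The documents do not support a charge of invalid or biased allocation. Assignment from the block list is random, and the loss is one of precision: roughly 2% to 5.5% of the standard error under the assumed 60% share and 20- to 30-point gaps. The protocol should be corrected before the list is generated, but the point does not threaten the comparison.

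**What to change.** Choose one method and make the two subsections agree.

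- **Preferred.** Delete the minimisation sentence under Allocation Concealment. Generate the permuted-block list within one named factor already known from the baseline survey, for example 3 versus 4–5 MetS components, with a separate envelope series per stratum. Include that factor, as recorded in the survey and used for allocation, in the primary between-arm analysis of MetS status. Do not add enumeration area with blocks of 8: two levels by five areas makes 10 strata of about 12 women, with a between-arm size difference of SD about 4.8 and 95th percentile about 10 women, and exact 60:60 in only 17% of runs. That would strain the planned five groups of 12.
- **Alternative.** Keep minimisation. Delete the block list and the sequential hand-out of envelopes, name the factors, add a random element, and adjust the primary analysis for the same factors.
- **If neither is done.** Delete the balance claim under Sequence generation, and still adjust the primary analysis for baseline component count.

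The cost is protocol wording and one run of the list by the biostatistician. With one two-level factor the arms may differ from 60:60 by a few women, at worst 56:64.

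### Consent and baseline assessment come after allocation, and women are traced once named lists by arm exist, so refusals and exclusions can differ between arms

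*Protocol*

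**What the plan says.** Under Randomization: Allocation Concealment, the units allocated are survey names, not consented women: "The numbered envelopes will be distributed in sequence from 1 to 120 to a list of names from the baseline survey diagnosed with Metabolic Syndrome". On consent the section says: "Due to practical reasons, we shall obtain informed consent after the randomization process". Women are then sorted by arm, and "two allocation lists will be generated with control and intervention groups". The next step is: "The principal investigator will then follow up and identify the study participants in their respective villages, with the assistance of the village chairpersons". The same section also says: "The study coordinator who will be blinded to the randomisation allocation list will enrol the participants".

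Sample selection describes women with Metabolic Syndrome (MetS) from the survey who "will be followed up in the community, screened and invited for participation in the study at baseline". Section 3.9 (Data Collection Procedures) lists consent together with the baseline questionnaires, measurements and blood tests. Section 3.3 includes the principal investigator in the team that provides the nutrition and motivational components.

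Two allocation methods are named. Randomization: Sequence generation says "a randomisation list of permuted blocks of size 8 with an allocation ratio of 1:1 will be generated". Allocation Concealment says "Random allocation will be conducted with minimization algorithm centrally in a single step to obtain two lists of nominative data". Sequence generation refers to stratifying variables but names none.

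**The concern.** Randomisation makes the two sets of 60 names comparable. The analysis, however, can use only women who agree, pass screening and give data. If those steps come after the arm is fixed, and the arm may be known to whoever approaches the woman or to the woman herself, the two analysed groups need no longer be comparable.

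There are two routes to a difference. The first is refusal. The intervention asks for 12 weekly sessions plus monthly motivational sessions. The control arm has baseline and end-line assessments and referral to usual care. The second is exclusion. Some criteria in section 3.4 need judgement, notably the one on diseases that the sessions might aggravate, and that criterion comes to mind more readily for a woman listed for the sessions.

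A bias of this kind is hard to repair in analysis, because a woman who refuses at this stage has no trial baseline or outcome data.

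**Working it through.** **1. Order of events.** Reading Allocation Concealment with section 3.9 and Sample selection:

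- survey names are put in random order and allocated;
- lists by arm are produced;
- the principal investigator traces the women;
- consent and baseline measurement take place together.

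The position of consent is stated outright. The position of the remaining eligibility checks is inferred: MetS was diagnosed in the earlier survey, and Sample selection places screening and invitation at the community follow-up.

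**2. The plan's own allowance.** Section 3.7 goes from 98 to 104 (design effect) to 120, with 10% for dropout and failure to consent combined. Check: 104/(1 − 0.10) = 115.6, so 116; the stated 120 is on the safe side. Sequence generation allocates those 120 as 60 and 60. Failure to consent is therefore expected among women already allocated.

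**3. Possible size.** The Protocol gives no refusal rate by arm and no remission rate, so these inputs are assumptions: no true effect; remission of MetS at 3 months 20% overall and 5% among refusers; 5% refusal in the control arm. With refusal r,

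remission among consenters = (0.20 − 0.05r)/(1 − r).

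Control arm: (0.20 − 0.0025)/0.95 = 20.8%, with 57 of 60 remaining.

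| Intervention refusal | Remission among consenters | Women left | Spurious difference |
|---|---|---|---|
| 10% | 0.195/0.90 = 21.7% | 54 | +0.9 points |
| 20% | 0.190/0.80 = 23.75% | 48 | +3.0 points |
| 30% | 0.185/0.70 = 26.4% | 42 | +5.6 points |

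A plus sign favours the intervention. If remission among refusers is 15%, the formula becomes (0.20 − 0.15r)/(1 − r). The control arm is then 20.3%, and the 20% and 30% rows fall to +1.0 (21.25%) and +1.9 (22.1%).

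**4. Outer range.** Suppose refusal occurs only in the intervention arm and every refuser still has MetS at 3 months. With true prevalence p, the observed intervention prevalence is (60p − 60r)/(60 − 60r).

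- p = 0.95, r = 10%: 51/54 = 0.944, a spurious difference of 0.6 points.
- p = 0.75, r = 30%: 27/42 = 0.643, a spurious difference of 10.7 points.

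**5. Bias or power?** The rates behind the 98 are not stated. One pair that reproduces it is 0.95 against 0.75, two-sided 5%, 80% power: [1.960·√(2·0.85·0.15) + 0.842·√(0.95·0.05 + 0.75·0.25)]²/0.20² = 48.8, so 49 per arm and 98 in total. With that pair, 60 controls and losses of 10%, 20% or 30% in the intervention arm only, power is 86%, 84% or 82%. The main risk is bias, not loss of power.

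**The case against.** The strongest reply is that the Protocol does protect allocation. Names are put in random order and allocated centrally in one step, envelopes are sealed and opaque, the enrolling coordinator is blinded to the list, and so are data collectors and laboratory staff (Blinding). A reader might infer that concealment is lost altogether. That is too strong: nobody can steer a given woman into an arm. What these steps do not protect is her entry to the analysed groups after the arm is fixed.

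A reader might also infer that whoever applies the exclusions knows the arm. No section says who applies them. The principal investigator's stated task is to trace and identify, and consent taken at baseline data collection could fall to blinded staff. What stands is the contradiction: one section has women traced from lists by arm by a member of the delivery team and also enrolled by someone blinded to the list.

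Other stronger readings fail too. Controls are not asked for nothing: they give fasting blood and complete questionnaires twice. Refusal of 20% or 30% in one arm exceeds the plan's combined 10%, so the larger figures above are scenarios, not expectations. Baseline measurement after allocation is a lesser worry, given blinded assessors and an earlier survey diagnosis.

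The Protocol gives practical reasons for the order without saying what they are. They may be real, and the fix allows for that.

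**Conclusion.** The point holds. Consent and baseline measurement follow allocation by the Protocol's own words, and the remaining screening does so by inference. Refusals after allocation are built into the sample size, and burden differs between arms. Who approaches and enrols women, and whether they know the arm, is stated inconsistently.

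The size is unknown. Under the assumptions shown it runs from under 1 point to about half of the planned 20-point difference, and at refusal near the plan's own 10% allowance it is small. The case therefore rests on the avoidable exposure to bias, not on any one figure.

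Separately, permuted blocks and minimisation are different procedures, and the Protocol names both.

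**What to change.** **Order.** Trace, screen, obtain consent and take baseline measurements first; only then open the next sealed envelope. Do not release lists by arm beforehand, and state who approaches, screens and enrols. The target of 120 randomised stands. The number to approach is 120/(1 − r): 127, 134, 150 or 172 at an assumed 5%, 10%, 20% or 30% refusal or ineligibility. The staff and envelopes are the same. The cost is an amendment, re-sequenced field work, and some delay and renewed contact if central laboratory results are awaited.

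**If that order is not feasible.** Have staff unaware of the lists approach, screen and consent the women, and report and analyse all allocated women by arm as far as data allow. The Data Analysis rule that drops women attending under 60% of sessions would have to give way in that analysis.

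**Allocation method.** Reconcile permuted blocks and minimisation into one stated method, and name any balancing variables. Stratifying by enumeration area is optional, and equal numbers per area should not be assumed. If envelopes are opened in sequence, vary and conceal the block sizes, because the last allocations in a fixed block of 8 can be predicted in an unblinded trial.

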#### Blinding

Given the nature of the intervention, it may not be possible to blind the participants and the health care workers. However, the laboratory technicians and research assistants who will collect the data will be blinded to the group assignment.

#### Design and development of the training curriculum for the Intervention

Step 1: The principle investigator will conduct the design and development of the curriculum. Initially a desk review/literature review will be conducted in which materials on dietary intake and lifestyle behavioral change for management of Metabolic Syndrome among females of reproductive will be reviewed. Materials and documents from Ministry of Health, academic research institutions doing work related to MetS and nutrition and relevant articles will be reviewed. Key information and finding from study one (On factors associated with MetS) will also be incorporated in the desk review. This will generate information on good practices, training needs and competence gaps in delivery of nutrition education and counselling which will be used to draft a curriculum framework (outlining main nutrition education topics on appropriate dietary intake and lifestyle behavioral change for Metabolic syndrome to be undertaken and when offered during the 12 weeks of the intervention) and then an initial draft curriculum developed.

Step 2: The initial draft curriculum will be shared with the content experts (nutritionists and public health experts) from Makerere University School of Public Health, in the Ministry of Health, Uganda for input. Following their feedback, revisions and amendments to the curriculum will be made. The investigator will then review and refine the curriculum based on the feedback to develop the draft curriculum which will be field tested in a sub-county in Kampala and necessary corrections made based on feedback from the pre-test. After corrections have been made, the final curriculum document will then be used to train the healthcare workers and nutritionists for 18 hours (3 days), in preparation for the intervention.

## Figure 1: Flow diagram of study participants

#### **3.8 Quality Control Measures**

Training of study team members: The study team members will undergo 18 hours of training on the study curriculum. This will be additional training to the initial 3 days of training on Metabolic syndrome that the study team underwent. The goal of this training will be for the study team to provide standardized intervention.

#### Adherence to Study Intervention:

Adherence to the intervention will be monitored through evaluating questionnaires and meeting attendance registration, use of paper reminders provision of information about study objectives and planned meeting schedules, and reinforcement of the need for compliance during follow-up meetings.

#### Minimizing Loss to Follow-Up:

We will try to minimize loss to follow-up. Participants will be given verbal reminders after each training session. The

As part of an incentive for continued participation, participants will participate in the supervised group sessions only during the weekends so that their usual working routines are not disrupted.

Motivation counselling will be provided by skilled community psychologists to motivate participants to attend the weekly sessions.

**Data collection**: The study will employ 2 laboratory technicians to draw off blood and 6 trained data collectors/research assistants (female nurses and graduate nutritionists), who will be trained for 3 days on the study protocol and how to use ODK to collect data and sending data to the servers at base line and end line of the study. The data collection tools will be field tested from a nearby district to the study districts.

**Intervention implementation:** The study will use 5 masters of public health nutrition trainees with a nutrition background at undergraduate to conduct the group nutrition education training for the study participants. 5 sports scientists will provide physical activity sessions For the group motivation interviewing sessions, 5 qualified health workers with training in motivation interviewing and nutrition will undertake the group motivation interviewing sessions.

